2. TIME AND EVENTS SCHEDULE – AFTER DISCHARGE FROM HOSPITAL

Note: This Time and Events Schedule should start with the study day number following the day of discharge from the hospital (for example: subjects discharged on Study Day 3 would start with Day 4 procedures on this schedule). After subjects are discharged, the remainder of the study visits should be carried out as outpatient visits (preferably on-site or, if not feasible, at the subject's home) or by telephone follow-up as indicated in the table below. Every effort should be made to perform all of the assessments as outlined below (either on-site or at the subject's home), if practically feasible. In case of readmission to the hospital, subjects will continue to follow this Time and Events Schedule until the end of the study.

Phase Day	Treatment ^{a,b} 2/3/4/5	Follow-up ^b						
		6 ^c	7-9	10 +/-1 Day	11-13	14 +/-1 Day	15-27	28 +/-1 Day
	Phone Follow-up ^e						Phone Follow-up ^f	Safety Follow-up Visit / Final Study Visit ^b
Clinic or home visit		X		X		X		X
Administration								
Administration of study drug ^{a,g}	X							
Virology								
Nasal MT swab for central testing ^h		X ⁱ		X		X		
Efficacy/Safety								
Vital signs/pulse oximetry ^j		X						X
Physical exam								X
Symptom-directed physical exam		X		X		X		
12-lead ECG ^k								X
Pregnancy test (female subjects of childbearing potential)	X ^l							X
Influenza Symptom Diary ^{s,t}		2x daily through the Final Study Visit/Safety Follow-up Visit ^d						
Assessment of daily activities resumption ^{m,t}		1x daily through the Final Study Visit/Safety Follow-up Visit ^d						
PGIS ^{n,t}		1x daily through the Final Study Visit/Safety Follow-up Visit ^d						
PGIC ^{o,t}		X ^d				X ^d		X
EQ-5D ^{p,t}		X ^d				X ^d		X
Hematology, chemistry		X ^q				X ^q		X ^q
Urinalysis		X				X		X
Pharmacokinetics		X ⁱ						
Taste and swallowability	X ^r							
Adverse events recording	X	X		X		X	X	X
Prestudy and concomitant medication recording	X	X		X		X	X	X

Abbreviations: ECG: electrocardiogram; EQ-5D: European Quality of Life 5 Dimensions; MT: mid-turbinate; PGIC: Patient Global Impression of Change; PGIS: Patient Global impression of Severity.

- a. If the subject is discharged during study treatment, he/she will receive study drug for at-home use.

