- S/P cardiac arrest
- Cardiogenic Shock
- Acute myocardial infarct with complications
- Cardiac tamponade
- Acute congestive heart failure
- Acute or imminent respiratory failure
- Hemodynamic instability
- Diabetic ketoacidosis complicated by hemodynamic instability, altered mental status, respiratory insufficiency, or severe acidosis
- Other conditions requiring specialized equipment and/or staff competencies only available in the ICU

3. Non-ICU hospitalization, requiring supplemental oxygen

Subject met either of the 2 following criteria:

- Non-ICU hospitalized on the day of assessment (including readmittance), not ready for discharge during the whole day of assessment, as judged by the investigator and supplemental oxygen is required by the subject
- In the ICU but there is no medical reason to be in the ICU during the day of assessment, and supplemental oxygen is required by the subject

Requiring supplemental oxygen is defined by:

- Receiving supplemental oxygen through a face mask or nasal cannula and not being able to sustain a blood oxygen saturation of $\geq 94\%$ when breathing room air for 15 minutes at any time on the day of assessment.
- If supplemental oxygen was provided chronically pre-influenza infection (based on medical history), that amount of supplemental oxygen is exceeded to prevent hypoxia, tachypnea or dyspnea at some point on the day of assessment.
- Not receiving supplemental oxygen and either:
 - Having a blood oxygen saturation of $< 94\%$ when breathing room air for 15 minutes at any measurement on the day of assessment, or
 - In case of known pre-influenza $SpO_2 < 94\%$ (eg, due to COPD), the current blood oxygen saturation on room air is lower than pre-influenza infection levels by at least 3%.

2. Non-ICU hospitalization, not requiring supplemental oxygen

Subject met either of the 2 following criteria:

- Non-ICU hospitalized on the day of assessment (including readmittance) and not ready for discharge during the whole day of assessment, as judged by the investigator
- In the ICU but there is no medical reason to be in the ICU during the day of assessment

1. Not hospitalized

Any of the following:

- Discharged from the hospital before the day of assessment
- Hospitalized at the day of assessment but ready for discharge on both the day of assessment and the day prior, as judged by the investigator (eg, in case of lack of bed availability in a skilled nursing facility, lack of social support at home).

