ATTACHMENT 6. : HRS DERIVATION

The HRS categories should be evaluated from 6 to 1. First check if the subject falls in category 6 (has the subject died?) if not then we evaluate category 5, if not 5 then evaluate category 4 and so on.

The HRS is evaluated at baseline and per day, relative to the first study drug intake.

The baseline HRS is covering the full baseline/screening/day 1 visit which can occur on 2 days.

Timing of first study drug intake is not taken into account.

Note:

- VSOXYSAT is assessed 3 times per day (or per baseline visit). In case one of the assessments says 'N' then the final result for that day (or baseline visit) is 'N', else if one of the assessments is 'NA' then the final result is 'NA' else if one of the assessments is missing then final result is missing.

So a combination of 'Y', "", "N" → result ='N'

'Y', "", "NA" → result ='NA'

'Y','Y','' → result =''

'Y','Y','Y' → result ='Y'

On the baseline visit, on days at or after HO end date or on the day of discontinuation it might be that less than 3 assessments are done. Therefore, take only the records into account from the dataset on those days as planned. The same rules above apply to derive the final result per day when more than 1 assessment is collected.

- In case the subject withdrew from the study, the HRS will be set to missing from the next day onwards.
- In case of chronic oxygen use and multiple CMARTN values on a day we consider the worst value: In case one of the values is 'N' then final result for that day (or baseline visit) is 'N', else if one of the assessments is missing then final result is missing.
- The list of types of supplemental oxygen and invasive mechanical ventilation can be extended depending on the medical review (see DPS part 2 or Excel sheet of the medical review)
- The list of hospitalization terms (i.e.: ICU or WARD) can be extended depending on the medical review (see DPS part 2 or Excel sheet of the medical review).
- If the Subjects has no HO data, the subject is considered to be in the hospital during the trial. All other aspect of the HRS will be evaluated according to the derivation below.
- In case the readiness for discharge (RDISHOSP) is assessed more than once per day (baseline visit) we consider the worst value: in case one of the values is 'N' then the final result of that day (or baseline visit) is 'N'

Some clarification is required for following categories:

6. Death

When DM.DTHDTC<=(date of assessment)

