5. Requiring invasive mechanical ventilation;

When CMSTDTC<=(date of assessment) <=CMENDTC where CMADMTP="INVASIVE MECHANICAL VENTILATION"

And CMADMDS in ('Through Endotracheal tube' 'Through Tracheostomy tube' or 'Through ECMO')

4. Admitted to the ICU;

From the HO data set:

hostdy <=(day of assessment)<=hoendy
hoterm = 'ICU'

From the SS data set:

SSTESTCD= 'REQICU' and SSSTRESC='Y'
Or SSTESTCD= 'REASICU' and SSSTRESC='Y'
Or both REQICU and REASICU is missing and NOT (RDISHOSP = 'Y' on the day of assessment and RDISHOSP = 'Y' on the day (baseline visit) before)

OR

From the HO data set:

hostdy <=(day of assessment)<=hoendy
hoterm = 'WARD'

From the SS data set:

SSTESTCD='REASICU' and SSSTRESC='Y'
OR
SSTESTCD='REQICU' and SSSTRESC='Y'

3. Non-ICU hospitalization, requiring supplemental oxygen

Non-ICU hospitalization:

hostdy <=(day of assessment)<=hoendy
hoterm = 'Hospital inpatient Department (WARD)'
NOT (RDISHOSP='Y' on the day of assessment and RDISHOSP='Y' on day(baseline visit) before)

OR

hostdy <=(day of assessment)<=hoendy
hoterm = 'ICU'
NOT (RDISHOSP='Y' on the day of assessment and RDISHOSP='Y' on day(baseline visit) before)

OR

(day of assessment)=hoendy+1
RDISHOSP='N' on day(baseline visit) before

OR

In case re-hospitalization occurred (there is a day between the HOENDY of the previous record and HOSTDY of the next record)
(day of assessment) =HOSTDY (of the re-hospitalization)
NOT (RDISHOSP='Y' on the day of assessment and RDISHOSP='Y' on day(baseline visit) before)

AND

Requiring supplemental oxygen:

'Receiving supplemental oxygen through a face mask or nasal cannula and not being able to sustain a blood oxygen saturation of $\geq 94\%$ when breathing room air for 15 minutes at any time on the day of assessment.'

FAOBJ=CHRONIC OXYGEN USE and FAORRES='N'

CMADMTP in ("Non-Invasive Mechanical Ventilation", "Nasal Cannula", "Venturi Mask", "Simple Face Mask", "Nonrebreathing Face Mask with Reservoir and One-Way Valve".)

CMTRT=SUPPLEMENTAL OXYGEN and CMSTDTC <= date of assessment <= CMENDTC

VSOXYSAT in ('N' 'NA') at any time during the day of assessment (OR is missing)

OR

'If supplemental oxygen was provided chronically pre-influenza infection (based on medical history), that amount of supplemental oxygen is exceeded to prevent hypoxia, tachypnea or dyspnea at some point on the day of assessment.'

FAOBJ=CHRONIC OXYGEN USE and FAORRES='Y'

CMARTN = 'N'

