CMADMTP in ("Non-Invasive Mechanical Ventilation", "Nasal Cannula", "Venturi Mask", "Simple Face Mask", "Nonrebreathing Face Mask with Reservoir and One-Way Valve".) and CMTRT=SUPPLEMENTAL OXYGEN and CMSTDTC <= date of assessment <= CMENDTC

OR

'Not receiving supplemental oxygen and Having a blood oxygen saturation of <94% when breathing room air for 15 minutes at any measurement on the day of assessment'

No record in cm with oxygen supplementation

VSOXYSAT='N' at any time on the day of assessment OR [VSTESTCD='OXYSAT' and VSORRES<94% and VSOXSMRA='Y']

OR

'Not receiving supplemental oxygen and in case of known pre-influenza SpO2 <94% (eg, due to COPD), the current blood oxygen saturation on room air is lower than pre-influenza infection levels by at least 3%.'

No record in cm with oxygen supplementation

VSEVINTX= PRE-INFLUENZA INFECTION and VSTESTCD='OXYSAT' and 'VSORRES<94% and VSRMAIR='Y'

VSORRES and VSTESTCD=OXYSAT (of day of assessment) < [VSORRES and VSEVINTX= PRE-INFLUENZA INFECTION and VSTESTCD='OXYSAT' and VSRMAIR='Y' - 3]

2. Non-ICU hospitalization, not requiring supplemental oxygen

hostdy <=(day of assessment)<=hoendy

hoterm = 'Hospital inpatient Department (WARD)'

NOT (RDISHOSP='Y' on the day of assessment and RDISHOSP='Y' on day(baseline visit) before)

hostdy <=(day of assessment)<=hoendy

hoterm = 'ICU'

NOT (RDISHOSP='Y' on the day of assessment and RDISHOSP='Y' on day(baseline visit) before)

OR

(day of assessment)=hoendy+1

RDISHOSP='N' on day(baseline visit) before

OR

In case re-hospitalization occurred (there is a day between the HOENDY of the previous record and HOSTDY of the next record)

(day of assessment) =HOSTDY (of the re-hospitalization)

NOT (RDISHOSP='Y' on the day of assessment and RDISHOSP='Y' on day(baseline visit) before)

1. Not hospitalized

Some examples

Discharge against medical advice

If a subject is discharged 'against medical advice' on the day prior to the day of assessment, the subject will be considered as hospitalized (evaluating the others aspects of the HRS to define the correct category, e.g.: requiring supplemental oxygen, on the day of assessment)

We have a discharged against medical advice if on the day the subject is discharged (according to the HO dataset) the investigator indicated he is not ready and his SS status is discharged,

	Day 3	Day 4	Day 5	Day 6	Day 7	Day 8
Status (HO)	Hospitalized	Hospitalized	Hospitalized	Discharged	Home	Home
Case 1						

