ready (SS)	Not ready	Not ready	Not ready	Not ready	--	--
Status(SS)	hospitalized	hospitalized	hospitalized	Hospitalized	discharged	--
Against medical advice?					NO	
HRS	>1	>1	>1	>1	>1	HOME
Case 2						
ready (SS)	Not ready	Not ready	Not ready	Not ready	Ready	--
Status(SS)	hospitalized	hospitalized	hospitalized	Hospitalized	discharged	--
Against medical advice?					NO	
HRS	>1	>1	>1	>1	>1	HOME
Case 3						
ready (SS)	Not ready	Not ready	Not ready	Not ready	Not ready	--
Status(SS)	hospitalized	hospitalized	hospitalized	Hospitalized	discharged	--
Against medical advice?					NO	
HRS	>1	>1	>1	>1	>1	HOME
Case 4						
ready (SS)	Not ready	Not ready	Not ready	Not ready		--
Status(SS)	hospitalized	hospitalized	hospitalized	Discharged		

Against medical advice?				YES		
HRS	>1	>1	>1	>1	>1	Missing
Case 5						
ready (SS)	Not ready	Not ready	Not ready	Ready	--	--
Status(SS)	hospitalized	hospitalized	hospitalized	discharged		
Against medical advice?				NO		
HRS	>1	>1	>1	>1	HOME	HOME
Case 6						
ready (SS)	Not ready	Not ready	Not ready	Ready	--	--
Status(SS)	hospitalized	hospitalized	hospitalized	hospitalized	discharged	
Against medical advice?				NO		
HRS	>1	>1	>1	>1	HOME	HOME
Case 7						
ready (SS)	Not ready	Not ready	Ready	Ready	--	--
Status(SS)	hospitalized	hospitalized	hospitalized	hospitalized	discharged	
Against medical advice?				NO		
HRS	>1	>1	>1	HOME	HOME	HOME
Case 8						
ready (SS)	Not ready	Not ready	Not ready	--	--	--
Status(SS)	hospitalized	hospitalized	discharged	--	--	
Against medical advice?			NO			
HRS	>1	>1	>1	>1	HOME	HOME

Only in case 4 above we have a discharge against medical advice which would lead to missing values from day 8 onwards. The HRS on day 7 is defined by the other aspects of the HRS (requiring oxygen, ICU,..) on day 7 and not copied from day 6.

Requiring supplemental oxygen

	Case 1	Case 2	Case 3	Case 4	Case 5	Case 6
supplemental oxygen (CM)	YES	YES	NO	NO	NO	NO
Chronic oxygen use	No	yes	Not used	Not used	Not used	Not used
returned to prior level?	Not used	N	Not used	Not used	Not used	Not used
pre influenza infection levels	Not used	Not used	Not used	Not used	Not used	93
Oxysat record < pre-influenza level at any moment during the day	Not used	Not used	Not used	Not used	Not used	yes
sustain >94% Oxy sat (VSOXYSAT)	N' missing or 'NA'	N' missing or 'NA'	N' at any time during the day	Missing or NA	YES	Not used
Oxysat record <94% at any moment during the day	Not used	Not used	no	yes	yes	Not used

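### Day 6 recovery scale, category 3: the pre-influenza SpO2 limb exempts no one, so an off-oxygen inpatient back at a usual SpO2 below 94% is scored as requiring oxygen

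*Protocol*

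**What the plan says.** The primary endpoint is the six-category hospital recovery scale on Day 6. Categories are tested from worst to best, so category 3 (non-ICU, requiring oxygen) is assigned before category 2 (non-ICU, not requiring oxygen) is considered.

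For a subject not receiving oxygen, Protocol 9.2.1.1 and SAP 5.2.1 give two limbs introduced by 'either'. Limb (a) is SpO2 below 94% "when breathing room air for 15 minutes at any measurement on the day of assessment, or" limb (b), for a known pre-influenza SpO2 under 94%: "the current blood oxygen saturation on room air is lower than pre-influenza infection levels by at least 3" per cent.

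SAP Attachment 6 codes limb (a) as "VSOXYSAT='N' at any time on the day of assessment OR [VSTESTCD='OXYSAT' and VSORRES<94% and VSOXSMRA='Y", with no term for the pre-influenza level. When the sustain-94% question is asked several times in a day, one negative answer decides: "In case one of the assessments says 'N' then the final result for that day (or baseline visit) is 'N". Limb (b) is a separate OR branch. Its current value must lie strictly below a bracket ending "VSTESTCD='OXYSAT' and VSRMAIR='Y' - 3", that is, below the usual level minus 3.

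Other sections treat subjects with a usual SpO2 below 94% differently:
- Protocol 4.1, inclusion criterion 5, requires a fall of at least 3% from the subject's own level.
- Protocol 9.6.4 makes the pre-influenza level the oximetry target in place of 94%.
- Clinical and respiratory response (Protocol 2.1.2 and 11.4; SAP 5.3.1.1, Table 4) count return to the pre-influenza level as resolution.

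**The concern.** A limb written specifically for patients with chronically low saturation should change how they are scored. As joined, it does not.

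Criterion 5 makes these subjects, if not ventilated, enter with a fall of at least 3% from their usual level. Those off oxygen and not needing ICU-level care therefore start in category 3. If such a subject is back at the usual level on Day 6 but still an inpatient, the score is 3 again. The boundary between categories 2 and 3 cannot register that recovery, although the response criteria would accept the same reading as resolved. This affects the primary endpoint, and the same derivation supplies the baseline category used as a covariate (SAP 5.2.3).

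**Working it through.** **Inputs.** Limb (a): reading c < 94. Limb (b), text: u < 94 and u − c ≥ 3. Limb (b), code: c < u − 3. Here u is the known usual SpO2 and c the current room-air reading, both taken as integers, with 3% read as 3 points. Reading it as a relative 3% gives the same integer cut-off for u from 85 to 93, because 3% of u is then 2.55 to 2.79.

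**Does limb (b) add or exempt anyone?** If u ≤ 93, limb (b) requires c ≤ 93 − 3 = 90, which is below 94. Every reading that meets (b) therefore meets (a). On a grid of u = 80–93 and c = 75–100 (14 × 26 = 364 pairs), limb (b) adds 0 pairs and exempts 0. In the code, limb (b) lacks the room-air flag on the current value, so it could add a subject whose flag is missing. It still cannot exempt anyone.

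**Which readings are scored 3 although the subject is at or above usual?** These are u ≤ c ≤ 93, a count of 94 − u. Readings 1 or 2 points below usual also fail limb (b) and are scored 3 only through limb (a), which makes the count 96 − u.

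| Usual SpO2 | At or above usual, <94 | Count | Including 1–2 below usual | Count |
|---|---|---|---|---|
| 93% | 93 | 1 | 91–93 | 3 |
| 91% | 91–93 | 3 | 89–93 | 5 |
| 88% | 88–93 | 6 | 86–93 | 8 |
| 85% | 85–93 | 9 | 83–93 | 11 |

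**Could site practice rescue the rule?** No. If a site followed 9.6.4 and answered the sustain question positively against the usual level, the recorded room-air value below 94% would still trigger limb (a). Worked oxygen Case 5 in Attachment 6 shows this: a positive answer and one record below 94% give YES.

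**Who is affected?** Subjects off oxygen, not needing ICU-level care, and not judged ready for discharge on both that day and the day before. Subjects ready on both days score 1. Chronic oxygen users on oxygen and back at their prior level are handled separately (Case 12 returns NO).

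**Margin.** At u = 91 and c = 88 the text fires (91 − 88 = 3) but the code does not (88 is not below 91 − 3 = 88). Limb (a) currently hides this. Once the limbs are separated, a subject enrolled off oxygen exactly at the criterion 5 threshold would be baseline category 3 by the text and 2 by the code.

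**Is there a power argument?** The plan's sample size reproduces. For placebo 30/30/25/5/5/5 and odds ratio 0.62, the pimodivir distribution is 40.87/29.88/19.38/3.42/3.28/3.16, and the cubes of the mean category proportions sum to 0.0825. Then N = 12(1.960 + 1.282)² / [(ln 0.62)² × (1 − 0.0825)] = 601.4, against 600 stated. Power at 600 is 89.94%. With the odds ratio refitted, moving 20% of category 3 to category 2 in both arms gives 88.85%; moving 20% of category 2 to category 3 gives 88.48%. Modelled power falls slightly either way, so power favours neither rule.

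**The case against.** Much of the opposing case stands.

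- **The code follows the text.** A reader might infer that Attachment 6 departs from the protocol. It does not: it implements the literal either/or. The defect is in the definition, so correcting only the program would be wrong.
- **The worked cases do not show intent.** Oxygen Cases 6 and 8 state a pre-influenza level of 93 and mark the below-94% row as not used, which tempts a reader to conclude that substitution was intended. But Cases 3 to 5 mark the pre-influenza level as not used and return YES, and Cases 6 and 8 return YES under either reading. The table is also unreliable: Case 7 returns NO where Case 1 and the category 3 code, which accepts a missing sustain answer, return YES.
- **There is no proven third margin.** The row "Oxysat record < pre-influenza level at any moment during the day" looks like another threshold, but it may be only a loose label. The discrepancy that can be relied on is text against code.
- **Recovery is not invisible.** Only one of five cut-points is affected. Time to clinical response credits return to the usual level, and the fundamental scale, analysed on Day 6, scores an off-oxygen ward subject 2. These are real mitigations, but both analyses lie outside the confirmatory sequence in SAP 5.1.1, and neither alters the primary test.
- **The change is late.** SAP Amendment 1 is dated 1 July 2020, after the pre-interim cut-off of 28 February 2020 (SAP 2.3), and pre-interim p-values enter the final combination test (SAP 5.1.2). This is a genuine cost and governs how any change is made.

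**Conclusion.** The point holds as a misclassification between categories 2 and 3. For off-oxygen inpatients with a known usual SpO2 below 94%, return to the usual level is scored as requiring oxygen, against the standard the documents apply to the same subjects in criterion 5, 9.6.4 and the response criteria. The logic needs no assumption about patient numbers; the counts of readings assume integer values.

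Three stronger conclusions are not supported. First, the rule is the same in both arms, so the misclassification is non-differential; neither bias towards an arm nor a power loss is shown. Second, the number of subjects affected cannot be derived, because the documents do not say how many have a known pre-influenza SpO2 below 94%. A fraction of all category 3 would be an invention and would include subjects on oxygen, whom this point does not concern. Third, the counts 3, 5, 8 and 11 do not all represent full recovery; only 1, 3, 6 and 9 of those readings are at or above the usual level.

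The passages should be reconciled before unblinding.

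**What to change.** Start with the wording of Protocol 9.2.1.1 and SAP 5.2.1, then carry it into Attachment 6 and its worked cases. For endpoint scoring only, using thresholds already in the documents, make the off-oxygen limbs mutually exclusive: the below-94% limb when pre-influenza SpO2 is 94% or higher or unknown, and the existing decline limb when it is known to be below 94%. Use one margin in text and code. State openly that it follows limb (b) and criterion 5 and differs from the return-to-level rule in 9.6.4 and Table 4: a subject 1 or 2 points below usual would score 2 while still unresolved under Table 4. Correct the inconsistent worked cases. No clinical threshold or management rule is proposed.

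Settle the derivation blind to treatment, apply it uniformly to baseline, pre-interim and post-interim subjects, and keep the scale as now coded as a sensitivity analysis.

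The cost is wording changes plus a reprogrammed and revalidated derivation; Attachment 6 already uses pre-influenza SpO2, so no new data are needed. The drawback is a late change to the primary endpoint. If the sponsor prefers to keep the primary derivation, the minimum is to reconcile the wording and the margin and to pre-specify the exclusive-limb scale as a sensitivity analysis.

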9.2.1.2. Complications of Influenza

From the moment subjects signing the informed consent form, any untoward event occurring with the subject is reported by investigators as AEs, refer to Section 12. For each reported event, investigators will be asked if they consider the event to be a complication of influenza. When answered yes, additional data related to that event is collected when available. A blinded Adjudication Committee (AC) will be established to adjudicate AEs as complications based on predefined criteria, refer to Section 11.14.

Based on the collected data, event identified as complications by investigators will be categorized into pulmonary versus extrapulmonary, major versus minor, as well as infectious versus noninfectious complications of influenza.

Pulmonary complications

- Respiratory failure: defined as either hypoxemic respiratory failure characterized by an arterial oxygen tension (PaO₂) lower than 60 mmHg with a normal or low arterial carbon dioxide tension (PaCO₂), or hypercapnic respiratory failure characterized by a PaCO₂ higher than 50 mmHg.
- Primary viral pneumonia: a progressive event involving the lower respiratory tract with bilateral and/or diffuse radiological findings. No bacterial agent is identified using sputum cultures.
- Secondary bacterial pneumonia (including pneumonia attributable to unusual pathogens): a clinical event compatible with lower respiratory tract involvement, with lobar infiltrates on radiological studies and/or microbiological isolate of a bacterial pathogen, including unusual pathogens.
- Exacerbations of chronic underlying pulmonary diseases such as COPD and asthma: subjects with documented medical history of COPD or asthma with a sudden worsening of symptoms and deteriorating respiratory function (the latter as evidenced by worsening hypoxia, tachypnea, etc.) The event must start before a full recovery from the influenza infection occurred.
- Bronchitis

Extrapulmonary complications

- Cardiovascular and cerebrovascular disease (eg, myocardial infarction, congestive heart failure, arrhythmia, stroke)
- Muscular disorders (eg, myositis, rhabdomyolysis)

- Central nervous system [CNS] involvement
- Acute exacerbation of chronic kidney disease
- Decompensation of previously controlled diabetes mellitus
- Other infections (eg, sinusitis, otitis)

